8 TOXICITIES AND DOSAGE MODIFICATION

This study will utilize the CTCAE (NCI Common Terminology Criteria for Adverse Events) Version 5.0

(https://ctep.cancer.gov/protocoldevelopment/electronic_applications/docs/CTCAE_v5_Quick_R efference_5x7.pdf) for adverse event and serious adverse event reporting.

8.1 Dose Modifications and Guidelines for Adverse Event Management

8.1.1 Dose Modifications

Dose levels:

- Dose level 1 25 mg BID
- Dose level 2 50 mg BID
- Dose level 3 75 mg BID
- Dose level 4 100 mg BID

If the dose is reduced because of toxicity, that dose should be maintained for the remainder of the trial and not re-escalated.

Toxicity Grade	What to do
Grade 1 – possibly, probably, or definitely related to study drug	For ALT/AST > 3x ULN, discontinue study medication.
	For all other grade 1 toxicities, monitor as needed until the problem has resolved (i.e., grade 0), stabilized (i.e., remains as grade 1), or is otherwise explained.
	If Grade 1 symptoms persist, the PI or Co-I will assess whether the dose should be reduced by 1 dose level or, if the patient is receiving dose level 1, whether the patient should discontinue study medication.
Grade 2 – possibly, probably, or definitely related to study drug	For total bilirubin > 2x ULN, discontinue study medication.
	For all other grade 2 toxicities, monitor as needed until the problem has resolved (i.e., grade 0), stabilized (i.e., remains as grade 1 or grade 2), or is otherwise explained.
	If Grade 2 symptoms persist, the PI or Co-I will assess whether the dose should be reduced by 1 dose level or, if the patient is receiving dose level 1, whether the patient should discontinue study medication.
Grade 3 – possibly, probably, or definitely related to study drug	If the patient was receiving dose level 1 at the time of toxicity development, the patient should discontinue study drug.
	For patients receiving dose level 2 or higher, if the symptoms resolve or improve to grade 1 or 2 within 7 days, the dose should be reduced by 1 dose level and the drug restarted at the time of symptom improvement. This dose is to be maintained if no further Grade 3 toxicity is noted.
	If the symptoms do not resolve or improve to grade 1 or 2 within 7 days, the patient can continue to hold study drug for another 7 days. If the symptoms resolve or improve to grade 1 or 2, the dose should be reduced by 1 dose level and the drug restarted at the time of symptom improvement. This dose is to be maintained if no further Grade 3 toxicity is noted. If

	the symptoms remain Grade 3 possibly, probably, or definitely related to the study drug, the patient should be permanently removed from protocol treatment.
	If upon restarting the medication at the lower dose the patient again experiences Grade 3 toxicity, the patient can again be given a 7-day drug holiday. Subsequently the patient may be rechallenged one dose level lower. If symptoms do not recur (i.e., if symptoms resolve to grade 0), the dose should be maintained. Alternatively, if Grade 1 or Grade 2 symptoms occur, the PI or Co-I will assess whether the patient should be removed from protocol treatment.
Grade 4 – possibly, probably, or definitely related to study drug	Study drug should be permanently discontinued.

Patients who experience hypersensitivity reactions to the study medication should discontinue the study medication.

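### Section 8.1.1 ties the ALT/AST and bilirubin stops to single grade rows, so a worse-graded ALT/AST event can draw a weaker instruction

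*Combined protocol and SAP*

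**What the plan says.** Section 8.1.1 sets the action for related toxicities by CTCAE version 5.0 grade.

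- **Grade 1 row.** It opens with "For ALT/AST > 3x ULN, discontinue study medication"; other Grade 1 events are monitored.
- **Grade 2 row.** It opens with "For total bilirubin > 2x ULN, discontinue study medication" and continues "For all other grade 2 toxicities, monitor as needed until the problem has resolved", or until it stabilizes or is explained. For lasting events, "If Grade 2 symptoms persist, the PI or Co-I will assess whether the dose should be reduced by 1 dose level", or, at dose level 1, whether to stop.
- **Grade 3 row.** It has no laboratory exception. At the lowest dose the drug stops: "If the patient was receiving dose level 1 at the time of toxicity development, the patient should discontinue study drug". At dose level 2 or higher the drug is held. If the event improves to Grade 1 or 2 within 7 days, or within a further 7 days, "the dose should be reduced by 1 dose level and the drug restarted at the time of symptom improvement". If instead "the symptoms remain Grade 3 possibly, probably, or definitely related to the study drug, the patient should be permanently removed from protocol treatment". After a second Grade 3 event and a 7-day holiday, "Subsequently the patient may be rechallenged one dose level lower".
- **Grade 4 row.** The drug is stopped for good.

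A sentence after the table stops the drug for hypersensitivity without reference to grade.

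**The concern.** In the Grade 1 and Grade 2 rows the liver stop is an exception, and the sentence that follows assigns everything else of that grade to monitoring. That ties each stop to its row. ALT/AST above 3x ULN is a mandatory stop in the mildest row, but the Grade 2 row does not mention ALT/AST and the Grade 3 row mentions no laboratory value at all. Staff who look up the action by grade could keep a patient on CBD, or restart it, at a transaminase level the protocol elsewhere treats as a reason to stop.

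What is at stake is participant safety under an ambiguous rule. Elevated transaminases are a listed reaction to this drug (section 3.1.4, Clinical Safety), and the same ALT/AST limit bars entry (section 5.2.3).

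**Working it through.** There is no plan figure to reproduce. The check is a reading of the table by row, a search for an overriding rule, and simple dose and calendar arithmetic.

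**1. Action by row, for values above the two thresholds**

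| Related event | Action as written |
|---|---|
| ALT/AST in the Grade 1 row, > 3x ULN | Stop |
| ALT/AST in the Grade 2 row | Monitor; investigator assessment if it persists; no required stop |
| ALT/AST Grade 3, dose level 2 to 4, improves to Grade 2 | Restart one level lower; no ULN value required |
| ALT/AST Grade 3, dose level 2 to 4, improves to Grade 1 but stays > 3x ULN | Restart rule and Grade 1 stop both apply |
| Bilirubin Grade 3, dose level 2 to 4, improves to Grade 2 but stays > 2x ULN | Restart rule and Grade 2 stop both apply |
| Second Grade 3 event after a restart at dose level 2 or higher | Rechallenge allowed after the holiday; the sentence names no grade or ULN value |
| Grade 3 at dose level 1, Grade 3 not improved, or Grade 4 | Stop |

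The fourth and fifth lines are conflicts between rows with no stated precedence. The second and third are cases where no stop is written. CTCAE cut-offs are not printed in the protocol, so I do not assign any particular laboratory value to a row.

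**2. Does another section repair it?**

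- 7.3.1 refers back to 8.1 for unacceptable toxicity. It also ends treatment after a 14-day delay, which limits the hold but sets no liver value.
- 11.1 lists liver tests without thresholds and leaves extra evaluations to clinical need or investigator discretion.
- 11.2 (stopping rules) is marked not applicable.
- 5.2.3 applies at entry only.

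None of these states an on-treatment liver stop that holds at every grade.

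**3. Doses on the restart path**

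Dose levels 1 to 4 are 25, 50, 75 and 100 mg twice daily, that is 50, 100, 150 and 200 mg/day.

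- From level 4: 200 to 150 mg/day (150/200 = 75%), then possibly 100 mg/day (100/200 = 50%).
- From level 3: 150 to 100 (100/150 = 67%), then possibly 50 (50/150 = 33%).
- From level 2: 100 to 50 (50%); a further Grade 3 event is then at level 1 and stops the drug.

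Under 7.1.2 the dose rises one level a week, so the planned level is min(week, 4). From week 4 a patient who tolerates the drug is at level 4, 200 mg/day.

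**4. Time to the next scheduled liver test**

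The section 9 calendar has on-treatment tests at week 4 (day 28, ±2), week 8 (day 56, −2 to +7) and week 15 (day 105, −2 to +7).

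- Week 4 to week 8: 56 − 28 = 28 days; range 54 − 30 = 24 to 63 − 26 = 37.
- Week 8 to week 15: 105 − 56 = 49 days; range 103 − 63 = 40 to 112 − 54 = 58.

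These gaps apply unless extra tests are ordered. They come from the calendar and not from the table; they show how long a patient could stay on drug between scheduled checks.

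**5. Background frequency**

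The Clinical Safety table gives elevated transaminases in 8% at 10 mg/kg/day, 16% at 20 mg/kg/day and 3% on placebo. The doses here are 0.625 to 4 mg/kg/day by the examples in section 2.2 (50 to 200 mg/day at 80 or 50 kg). These percentages cannot be carried over to this trial.

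**The case against.** The strongest reply is that both thresholds are open-ended. A value above 3x ULN is above 3x ULN at any grade, and a clinician who reads the whole table would stop the drug. That is probably what was meant, and it makes this a flaw of wording more than of intent. It does not settle the matter, because the table is organized for lookup by grade, the catch-all sentences confine each stop to its row, and no precedence is given where rows conflict.

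A second reply is that the Grade 3 restart text speaks of symptoms, and that section 16.5.3 counts abnormal laboratory values as adverse events only when they cause signs or symptoms or need therapy. On that reading the ULN lines are the laboratory rules and the restart text is for symptomatic events. This is a fair reading. But the table itself places ALT/AST and bilirubin among graded toxicities, and this reading would leave a Grade 3 laboratory event without a clear instruction.

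Third, there are real safeguards. Grade 2 events must be monitored as needed, and persistent ones go to an investigator. The second rechallenge is permissive; if Grade 1 or 2 symptoms then occur, the investigator must consider removing the patient. Investigators grade and attribute events, and the monitoring committee receives quarterly reports. All of that stands and reduces the practical risk. None of it sets a liver value that must be met before drug is continued or restarted.

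**Conclusion.** The concern holds. Followed by row, the written instruction for ALT/AST weakens as the grade worsens: stop in the Grade 1 row, monitor in the Grade 2 row, hold and restart in the Grade 3 row at dose level 2 or higher. For bilirubin the gap is narrower, a conflict between the Grade 2 stop and the Grade 3 restart.

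No event rate can be derived from the documents. At these low doses few of the 44 patients are likely to be affected, and no efficacy result changes. The conclusion rests on the text of the table and on the absence of an overriding rule elsewhere; it needs no assumption about CTCAE cut-offs. Confidence is high about what the table says and lower about how often staff would follow it literally. It should be corrected because it is a participant-safety rule that is wrong as written and cheap to put right.

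**What to change.** Take both thresholds out of the grade rows and state them once, next to the hypersensitivity sentence. Suggested wording: *Regardless of CTCAE grade or dose level, CBD is discontinued for ALT/AST > 3x ULN or total bilirubin > 2x ULN judged at least possibly related to study drug. This overrides the Grade 2 monitoring rule and the Grade 3 hold-and-restart rule.*

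If the investigators do want to allow rechallenge after a liver event, they should instead give the ULN values required before each restart, including the second.

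The cost is an amendment to the wording, with no new tests or visits. The downside is possibly a few more discontinuations. Those women still complete questionnaires through week 15 (section 9, footnote d), so they remain evaluable for the primary endpoint under section 12.2 if they complete the week 15 BPI.

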8.2 Supportive Care

All supportive measures consistent with optimal patient care may be given throughout the study.

8.3 Contraception

Only post-menopausal women (including those rendered postmenopausal with LHRH agonist therapy) are eligible for enrollment on this clinical trial. Postmenopausal is defined as one or more of the following:

- Absence of menses for at least 12 months
- Concurrent use of LHRH agonist therapy
- Prior bilateral salpingo-oophorectomy
- Serum or plasma concentrations of estradiol within postmenopausal range according to local lab values

9 STUDY CALENDAR

Required Studies	Screening ª	Baseline ^b	Weeks 1, 2, 3 (+/- 2 days) ^c	Weeks 4, 6 (+/- 2 days) ^c	Week 8 (-2, +7 days) ^c	Week 12 (+/- 2 days) ^c	Week 15 (-2, +7 days) ^{c, j}	Off Study (if prior to week 15) ^d
Informed consent	Х							
Medical History	Х							
Performance status ^m	Х							
Study visits ⁱ	Xd	Х			Х		Х	Х
Study coordinator phone calls ^{k, n}			Х	Х	Х	X	XI	XI
Vital signs ^e	Х							
Concomitant medications	Х	Х						
Adverse event assessment			Х		Х		Х	Х
Patient reported questionnaires ^f								
- BPI	Х	Х	Х	Х	Х	Х	Х	Х
- PROMIS		Х		X (wk 4 only)	Х		Х	Х
- GRC			X°	X (wk 4 only)	Х	Х	Х	Х
- METE		Х						
- FM Survey		Х					Х	Х
- CSQ		Х					Х	Х
- PANAS		Х					Х	Х
- PHQ9 ^p	Х	Х						
Phlebotomy ^g								
- Research	X ^r X				X X		Х	X X
 Clinical labs (aspartate aminotransferase, alanine aminotransferase, total 	X			X (wk 4 only)	Х		X	X
bilirubin, serum creatinine, complete blood count)								
Al therapy (standard of care)								•
Dispense study medicine		Х			Х			
CBD treatment ^h								
Medication log		Х			Х		Xi	Xi

a. Screening and baseline visits can take place on the same day. The informed consent can be completed either in person or remotely using SignNow. The BPI and PHQ9 will be completed after signing the ICF and can be completed by phone or electronically. Screening clinical lab studies must be completed within 28 days of registration; if they have already been completed for another reason (other than participating in this clinical trial) they do not need to be repeated.

b. Baseline visit can take place up to 4 weeks after the screening visit. Patient does not need to be seen by physician or advanced practice provider.

c. Timed based on initiation of CBD therapy.

d. This is the visit conducted at the time of AI discontinuation and/or study drug discontinuation as per section 7.3.1. These questionnaires should be completed within 3 business days of medication discontinuation. Patients will return remaining study drug and medication log at that study visit or at their next routine clinic

visit. Also if a patient discontinues study drug early, she should continue to complete questionnaires according to the study calendar through the 15 week timepoint.

e. Height and weight at screening visit. If these values have been documented in the medical record within 90 days they do not need to be repeated. f. Questionnaires will be completed electronically within 2 days before the scheduled visit, at the time of the visit, or within 2 days after the visit. It is preferable to have patients complete the questionnaires before or at each visit. Emailed reminders will be sent to patients from REDCap, and telephone reminders may also be used. If a scheduled visit is rescheduled after the questionnaires have been completed by the patient, they will not be considered out of window. If a patient declines to complete questionnaires electronically they may be completed on paper (baseline and week 8 and 15) or by phone (all timepoints).

g. It is preferred, but not required, that subjects fast for at least 8 hours prior to all blood collections (except for week 4). Time of blood draw and fasting status should be recorded. Details about research labs are in section 15.2.1.

h. Study medication should begin the first Wednesday morning after the baseline visit whenever possible. If the baseline visit is on a Wednesday, the participant can start the study medication the evening of the baseline visit. The medication should be taken with food twice a day approximately 12 hours apart.

i. At weeks 8 and 15 or off study, patient will meet with research study coordinator or otherwise return the medication log and/or remaining medication to the study team, depending on the timepoint. Patient does not need to be seen by physician or advanced practice provider. Patients will return medication log #1 at the 8 week study visit and return all remaining study drug and medication log #2 at the 15 week study visit, or at the off study visit if it occurs at a different time. If they forget to bring the medication and log to the visit, they should return the items at their next routine clinic visit.

j. For patients who wish to continue on therapy beyond the 15 week study visit, clinicians can provide a written prescription for off-label Epidiolex and/or provide recommendations for patients to go to local cannabis dispensaries in Michigan (since recreational cannabis is legal in this state), but drug will not be provided by the clinical trial following the week 15 study visit.

k. Study coordinator calls are to assess adverse events including suicidality and (if applicable) determine if there is a reason that the patient should not increase the dose by one dose level (as per section 8.1.1). If there is a question about whether the patient should or should not increase the dose, the study coordinator will contact the PI or Co-I. Also if patients have not completed questionnaires or if they decline to complete questionnaires electronically, the study coordinator should ask the questions by phone.

I. The study coordinator should follow-up with the patient by phone 30 days following the off-study visit to assess resolution of any AEs as per section 16.5. m. Performance status assessment at screening will be performed by a licensed physician (or physician's assistant or nurse practitioner) or registered nurse. Can have been performed up to 28 days before the screening visit, and can be performed during a virtual visit.

n. The study coordinator will ask about suicidal ideation on the phone calls using question 9 from the PHQ9: "How often have you been bothered by the following in the past week: Thoughts that you would be better off dead, or thoughts of hurting yourself in some way? Not at all, several days, more than half the days, nearly every day". If a patient reports anything other than "Not at all" to the question, the patient's oncology treatment team will be notified and the patient will be managed according to usual clinical protocols. If the treatment team is not available, the PI or another of the co-Is will be notified.

o. GRC should be completed at week 2.

p. The study coordinator should review the response to PHQ9 question 9 prior to dispensing the study medication to the patient. If the answer to the question is anything other than "Not at all", the study medication should not be dispensed and the patient's clinical team or covering provider should be notified immediately.

q. The screening study visit can be conducted virtually if the necessary patient information (other than lab results) can be found in the medical chart. Patient will need to undergo phlebotomy prior to enrollment in the study if screening lab studies have not otherwise been performed within the past 28 days.

r. If clinical lab studies do not need to be performed at screening because they have been performed within the 28 day window, the research blood specimens at screening can instead be collected at baseline.

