12.3.2 Exploratory endpoints

1. In this exploratory aim, all inflammatory markers and cytokine levels will be summarized using descriptive statistics at baseline and 15 weeks. The changes in inflammatory biomarkers will be assessed using one sample t-test of the difference (or sign test). Linear models will examine the association between the 8 and 15-week worst pain score (controlling for baseline worst pain score and change in pain worst pain) and baseline and 8 and 15-week inflammatory markers and cytokines. Normalizing transformations will be used if required.^{58, 59} We are limited in the number of covariates in each model based on sample size, so we will be careful of overfitting recognizing that patient and disease characteristics may be confounders in analysis. No correction for multiple comparisons will be applied based on the hypothesis generating nature of the aim.

2. In this exploratory aim, all questionnaire scores will be summarized using descriptive statistics at baseline and 15 weeks. The changes in survey responses will be assessed using one sample t-test of the difference (or sign test). We will use a linear model to examine the association between the 15-week worst pain severity (as measured by the BPI) and the baseline worst pain severity, and baseline and 15-week FM score. Similarly, separate models of the 15-week worst pain score will control for baseline worst pain severity and assess associations with baseline and 15-week PANAS scores and catastrophizing scores. We are limited in the number of covariates in each model based on sample size, so we will be careful of overfitting recognizing that patient and disease characteristics may be confounders in analysis. No correction for multiple comparisons will be applied based on the hypothesis generating nature of the aim.

3. We will report the proportion of individuals with undetectable levels of estrone and estrone sulfate at baseline and 15 weeks with corresponding exact binomial 95% confidence intervals. The exact levels of estrone and estrone sulfate at baseline and 15 weeks will be summarized using descriptive statistics.

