15.2 Correlative Studies

15.2.1 Blood correlative studies

The following samples will be collected:

- A. 10 cc blood will be collected for isolation of plasma at screening (or baseline as per study calendar), 8, and 15 weeks and stored in 500 ul aliquots at -80C.
- B. Blood will be collected in TruCulture system 1 ml tubes containing either LPS or media at screening, 8, and 15 weeks. Within 15 minutes of the blood draw the samples should be incubated at 37C for 24-48 hours, then the supernatant will be isolated and stored in 250 ul aliquots. (instructions for blood processing: https://myriadrbm.com/products-services/truculture/truculture-video/)

Samples will be collected at the time of standard of care phlebotomy whenever possible. Patients will fast for at least 8 hours prior to phlebotomy whenever possible. The study coordinator will record time of blood draw and whether or not patient was fasting.

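### Fasting status and draw time are recorded but not used in the marker-change tests, so a systematic shift in either between visits could not be told apart from a CBD effect

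*Combined protocol and SAP*

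**What the plan says.** Two sections govern sampling, and they agree. Footnote g of section 9 (Study Calendar) makes an 8-hour fast a preference, not a requirement, for every draw except week 4, and adds: "Time of blood draw and fasting status should be recorded". Section 15.2.1 has "Patients will fast for at least 8 hours prior to phlebotomy whenever possible", and then "The study coordinator will record time of blood draw and whether or not patient was fasting". No clock time is fixed; instead, "Samples will be collected at the time of standard of care phlebotomy whenever possible". The week-4 exception does not matter here, because section 15.2.1 lists research samples only at screening (or baseline), week 8 and week 15.

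The pre-treatment sample is normally a screening sample. Under footnote r, if clinical labs are already available, "the research blood specimens at screening can instead be collected at baseline".

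Exploratory item 1 of section 12.3.2 gives the analysis: "The changes in inflammatory biomarkers will be assessed using one sample t-test of the difference (or sign test". Linear models relating pain to markers follow. Neither part names fasting status or draw time, and no sensitivity analysis is planned. On adjustment the item says only "We are limited in the number of covariates in each model based on sample size", and that patient and disease characteristics may confound. Section 4.1 describes a single-arm trial, and exploratory objective 1 (section 1.3) is the impact of 15 weeks of CBD on these markers.

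**The concern.** By asking twice for fasting status and draw time, the protocol treats both as potentially relevant to the assays. The marker-change test then leaves them out. In a randomised trial, a drift in sampling conditions would tend to affect both arms and cancel. Here there is no second arm, so the mean paired difference contains the CBD effect plus the effect of any net change in sampling conditions.

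What is at stake is how the mechanistic results are read. A net shift could create an apparent marker change or hide a real one. Discordance that balances out across patients would leave the mean alone and only widen the spread of about 40 differences.

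**Working it through.** **Inputs from the documents.** 40 evaluable patients and a two-sided 5% level (section 12.2); one arm (section 4.1); a one-sample test of the paired difference (section 12.3.2). The plan states no power or effect size for the marker tests, so the primary endpoint's sample size is borrowed.

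**Plan's own figure.** Section 12.2 claims 80% power for a standardised effect of 0.45 with n = 40. A one-sample noncentral t calculation gives 79.3% at 0.45, and 80% power at 0.454 SD. The figure reproduces, and about 0.45 SD serves as the benchmark for an unadjusted one-sample test.

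**Assumed inputs.** The documents give neither of these:
- f, the net share of patients whose fasting status changes in one direction (share changing one way minus share changing the other way);
- d, the effect of that change on the marker, in SDs of the paired difference among patients with the same change in fasting status.

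**Bias.** With no CBD effect, the expected mean difference is f × d. The rejection rate comes from a noncentral t distribution with 39 degrees of freedom and noncentrality f × d × √40. Examples:
- f = 0.10, d = 0.5: shift 0.05 SD, noncentrality 0.05 × 6.32 = 0.32, rejection 6.1%
- f = 0.30, d = 0.5: shift 0.15 SD, noncentrality 0.95, rejection 15.2%
- f = 0.50, d = 0.5: shift 0.25 SD, noncentrality 1.58, rejection 33.8%

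This slightly overstates the rate, because a mixture of changed and unchanged patients adds f(1 − f)d² to the variance. Simulation that includes this (20,000 runs, n = 40, all discordance in one direction) gives these rejection rates for the planned t-test when CBD does nothing:

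| f | d = 0.2 | d = 0.5 | d = 0.8 |
|---|---|---|---|
| 0.10 | 5.1% | 5.7% | 6.9% |
| 0.25 | 5.9% | 11.0% | 19.9% |
| 0.50 | 9.2% | 31.4% | 63.8% |

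At f = 0 the rate is 5.0% whatever d is.

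**After adjustment.** Regressing the paired difference on change in fasting status and testing the intercept returns 4.7% to 5.2% in every cell. Coding matters: zero must mean no change. If the covariate is mean-centred, the intercept is again the raw mean change and the bias returns.

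**Price of adjustment.** With one-directional discordance, the intercept rests on the 40 × (1 − f) unchanged patients: 36, 30 and 20 for f = 0.10, 0.25 and 0.50. The effect detectable with 80% power (noncentral t, 38 degrees of freedom) rises from about 0.45 SD to 0.48, 0.53 and 0.64 SD. These figures adjust for fasting alone; adding draw time would cost somewhat more.

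**Draw time.** The same reasoning applies, with bias equal to the mean difference in draw time multiplied by the marker's slope on clock time. The documents supply neither, so no figure is given.

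**The case against.** A reader might infer that first samples will tend to be unfasted and week-15 samples fasted, and so that the plan will credit a fasting effect to CBD as an anti-inflammatory response. The documents do not support this. The fasting preference is worded the same for all research draws. Standard-of-care timing applies to all of them, not only the first. Study procedures are reviewed with the patient at consent (section 10.1), before any study sample; consent can be remote, and the first research sample can move to a baseline visit up to four weeks after screening. Consent and sampling on the same day is possible, but nothing shows it to be typical. CBD is to be taken with food twice a day, which could make fasting less common on treatment. Direction and size are both open.

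It is also fair to say that the aim is declared hypothesis generating, that any before-and-after comparison in one arm is exposed to uncontrolled influences, that covariates are limited by sample size, and that the recorded data would allow a later check. All of this stands. It rules out replacing the planned test, since the loss of precision is largest where discordance is largest. It does not answer the narrower point: these two influences, unlike most, are measured, and choosing how to use them after seeing the results would be a post hoc decision.

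**Conclusion.** The point holds conditionally. If fasting status or draw time differs systematically between the pre-treatment and week-15 samples, the unadjusted tests cannot separate that difference from a CBD effect. Over the assumed range (net discordance 10% to 50%, fasting effect 0.2 to 0.8 SD), the false-positive rate of the nominal 5% test runs from about 5% to about 64%. That range illustrates sensitivity and does not forecast what this trial will show, because neither input is in the documents. With similar fasting rates and draw times across visits there is no bias, only noise. The importance is low: the aim is exploratory, and BPI worst pain, the primary endpoint, is untouched.

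**What to change.** In section 12.3.2, exploratory item 1:
- Keep the planned one-sample t-test or sign test as the main analysis.
- Tabulate fasting status and draw time at screening/baseline, week 8 and week 15.
- Pre-specify two sensitivity analyses: (a) the same test restricted to pairs concordant on fasting status; (b) a regression of the paired difference on change in fasting status and difference in draw time, coded so that zero means no change and not mean-centred, with a test of the intercept.
- State that a marker change will be read as a possible CBD effect only if it is consistent across these analyses.

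If nearly all patients change fasting status, few concordant pairs remain and the intercept is poorly estimated; the table will show this and should be read with the results.

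Patients should not be asked to match the fasting state of their first sample. That would change study procedures and conflict with the stated preference for fasting whenever the first sample was unfasted.

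The cost is a little extra analysis on data already collected, and lower precision in the sensitivity results (detectable effect 0.48 to 0.64 SD instead of about 0.45 SD for 10% to 50% net discordance, adjusting for fasting alone). The planned test keeps its precision.
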